STUDY PROTOCOL AND STATİSTİCAL ANALYSIS PLAN

TİTLE: The Effect of Rubber Dam on Objective and Subjective Parameters of Stress During Dental Treatment in Children

DOCUMENT DATE: 14.11.2024

RCT: The study was approved by the Medical Ethics Committee of Izmir Katip Celebi University, under report No. 2024/0242

STUDY PROTOCOL:

This randomized, controlled, single-blinded study included 100 healthy, cooperative children (Frankl Scale, Rating 3-4) aged 6-12 years, classified as ASA I, with bilateral fully erupted mandibular first permanent molars requiring pit and fissure sealant procedures. The inclusion criteria were based on the International Caries Detection and Assessment System II, including deep and retentive pits and fissures, no restorations, and no evidence of carious lesions.

The study was planned as split mouth design: For each patient, one tooth was selected for rubber dam isolation, while the corresponding tooth from the opposite quadrant was chosen for cotton roll isolation. The Rubber dam application group divided also into two groups as topical EMLA application, and infiltration anesthesia application. Randomization was performed using manually generated sealed envelopes containing information about which isolation method and anesthesia technique would be used on which side of the jaw (right or left). Random numbers were written on separate papers, folded, and placed in opaque sealed envelopes. Each participant chose an envelope and was assigned the printed participant number. Each number identified the teeth included in the study, the isolation technique specified for each tooth, and the anesthesia method to be used during the rubber dam application.

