After the cleaning procedure, following the randomization result and determination of which isolation method would be applied to which side of the patient's jaw, to ensure that the local anesthetics used would not affect the patient's cooperation, in the first session, the selected tooth was isolated with standard cotton rolls and high-volume suction for the pit and fissure sealing procedure on one side of the patient. Cotton rolls were placed in both the lingual and mucobuccal side of the arch and the suction was positioned on the lingual side of the tooth. Cotton rolls were changed following enamel etching and, in every case, where they became excessively moisture throughout the treatment. The fissure sealant procedure was carried out following the manufacturer's instructions. Objective stress parameters (pulse rate, systolic blood pressure and diastolic blood pressure) for the children and the pulse rate of the operator were recorded at three different points. Systolic and diastolic blood pressure were measured using an automatic blood pressure monitor. Pulse rate was evaluated with a fingertip pulse oximeter. The operator's pulse rate was also recorded. Pain perception was assessed subjectively post-procedure using the Wong-Baker FACES Pain Rating Scale (WBFPRS) and Visual Analogue Scale (VAS). One week later, the patient was invited to a second appointment for the treatment of the corresponding tooth from the opposite side.

STATİSTİCAL ANALYSIS PLAN

All statistical analyses of the data were conducted using SPSS statistical software Version 21.0 (SPSS Inc., Chicago, IL, USA), with 0.05 selected as the level of significance (α). The normality test was conducted using Shapiro-Wilk and the Kolmogorov-Smirnov tests. Data were analyzed using Mann-Whitney U and independent samples t-tests. For within-group comparisons, Wilcoxon Signed Rank and the Friedman tests were employed.

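### For four measures read three times per session, the SAP states no between-condition test of change and no analysis that uses the split-mouth pairing for dam versus cotton roll

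*Combined protocol and SAP*

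**What the plan says.** The protocol describes a within-child comparison of isolation methods: "The study was planned as split mouth design: For each patient, one tooth was selected for rubber dam isolation", with the matching tooth on the other side isolated by cotton rolls. The dam condition is then split between children: "The Rubber dam application group divided also into two groups as topical EMLA application, and infiltration anesthesia application". The envelope assigns the anaesthesia method as well as the sides, so that second comparison is between different, randomised children.

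The child's pulse and systolic and diastolic pressure, and the operator's pulse, "were recorded at three different points". The document does not say when those points fall relative to isolation or anaesthesia. Cotton roll is used in the first session, and then: "One week later, the patient was invited to a second appointment".

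The Statistical Analysis Plan has two sentences on comparisons. The first is "Data were analyzed using Mann-Whitney U and independent samples t-tests". The second is "For within-group comparisons, Wilcoxon Signed Rank and the Friedman tests were employed". Neither names the groups, the time point, or whether the variable is a reading or a change. No change score, isolation-by-time term, adjustment for the first reading or mixed model is mentioned.

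**The concern.** The title asks what the dam does to stress during treatment. With three readings in each of two sessions on the same child, a natural answer is a within-child comparison of how the readings move in the two sessions. The SAP uses methods for repeated readings only inside a group. The tests it names for comparing groups are built for independent samples.

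Two things are at stake. First, if change over time is reported only within groups, a reader is left to compare a significant result in one session with a non-significant one in the other, and that is not a test of a difference. Second, unpaired tests on dam versus cotton roll would discard the pairing that the split-mouth design provides.

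**Working it through.** **Inputs from the document.** 100 children; significance level 0.05; three readings per session; dam versus cotton roll within child; EMLA versus infiltration between children. No power, SD, effect size or correlation is given, so the plan has no figure of its own to reproduce here.

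**Assumptions.** Two-sided tests; EMLA and infiltration 50:50; correlation ρ of a child's changes in the two sessions between 0 and 0.5 for step 1 and up to 0.7 for step 2; normal approximation.

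**Step 1. Separate within-group tests read as a comparison.** Let the true change be the same in both sessions and let each test have power p. Then P(exactly one significant) = 2 × [p − P(both significant)].

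- p = 0.80, ρ = 0: P(both) = 0.64, so 2 × (0.80 − 0.64) = 32%.
- p = 0.80, ρ = 0.5: P(both) = 0.687 (bivariate normal), so 2 × (0.80 − 0.687) = 23%.
- p = 0.50, ρ = 0: P(both) = 0.25, so 2 × (0.50 − 0.25) = 50%.
- p = 0.50, ρ = 0.5: P(both) = 0.333, so 2 × (0.50 − 0.333) = 33%.

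EMLA and infiltration involve different children, so the ρ = 0 figures apply: 32% and 50%. In simulation, a direct paired test of the difference in change (n = 100) rejected in 4.6-5.5% of trials.

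**Step 2. Unpaired tests on paired data, dam versus cotton roll.** In SD units of the variable compared, the true SE of the mean difference is √(2(1 − ρ)/100), while an unpaired test uses √(2/100) = 0.141. With no visit effect, the unpaired test's true size is 2 × [1 − Φ(1.96/√(1 − ρ))]. Power is for a true difference of 0.3 SD.

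| ρ | Size, unpaired | Power, unpaired | Power, paired |
|---|---|---|---|
| 0 | 5.0% | 56% | 56% |
| 0.3 | 1.9% | 58% | 72% |
| 0.5 | 0.6% | 59% | 85% |
| 0.7 | 0.03% | 62% | 97% |

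Ignoring the pairing therefore costs power and does not by itself inflate false positives.

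**Step 3. EMLA versus infiltration.** In simulation with 50 per arm, the independent t-test and Mann-Whitney test on change rejected in 4.3-5.2% of trials under no difference. They are valid for this comparison.

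**Step 4. What a change contrast can and cannot remove.** Suppose every second-visit reading shifts by 0.2 SD (assumed; range 0.1-0.3) and the dam has no effect. At ρ = 0.5 between the two sessions' readings, the true SE is 0.10 and the unpaired threshold is 1.96 × 0.141 = 0.277. A raw unpaired comparison at one time point then rejects with probability Φ((0.2 − 0.277)/0.10) = 22% (4-59% over the range). A paired raw comparison rejects in 52% (17-85%). Subtracting a reading taken before isolation cancels a shift that is the same at all readings. It does not cancel a visit effect on the response itself, such as habituation.

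**The case against.** A reader might infer that change is never compared between groups, or that the plan has no valid test of whether the dam or infiltration alters the stress response. The document does not support either. The named between-group tests take one value per child, and a change score is one value per child, so their use on changes cannot be excluded. The Wilcoxon signed-rank test listed as within-group might even mean dam versus cotton roll within child. For EMLA versus infiltration the groups are randomised and independent, and the named tests are valid on a later reading or on a change.

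A reader might also take the isolation-by-time contrast to be the right test wherever the three readings fall. It is not. If all three follow isolation, a constant rise under the dam gives zero interaction, and the level during treatment is the legitimate target.

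Finally, the plan nowhere says it will infer a difference from one significant and one non-significant result. The figures in step 1 measure the cost of that misreading and are not the error rate of a stated analysis. The figures in step 4 rest on assumed shifts and stem from the fixed session order, which is a separate design matter.

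All of this stands, and it limits the claim. It does not supply the missing analysis: no sentence in the SAP states a between-condition test of change or a paired comparison of the two isolation methods.

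**Conclusion.** The point holds as a gap in the stated analysis with a better method available on the same data. For the four repeatedly read measures, the SAP states no between-condition test of change and no analysis that uses the pairing for dam versus cotton roll. If unpaired tests are used there, power for a 0.3 SD difference is 59% instead of 85% at an assumed correlation of 0.5, with no loss at correlation 0. If the within-group tests are read comparatively, step 1 shows exactly one significant result in roughly a quarter to a half of trials with equal true change.

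For EMLA versus infiltration the gain is precision only. The point does not apply to the Wong-Baker and VAS scores, which are recorded once after each procedure. The sizes depend on the assumed correlations, power and two-sided testing. The absence of a stated analysis does not. The sponsor should make the change, which needs only revised SAP text and analysis of data already collected.

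**What to change.** 1. State when each of the three readings is taken relative to isolation and anaesthesia.
2. For each of the four measures, fit a linear mixed model with isolation, time point and isolation × time, and random child and child-by-session effects.
3. If the first reading precedes isolation, report the isolation × time contrast from the first reading to a named later point, with its 95% CI. A rank alternative is a Wilcoxon signed-rank test on each child's dam-minus-cotton difference in changes.
4. If it does not, report the within-child isolation difference at the named point with its 95% CI, because the interaction would miss a constant effect.
5. For EMLA versus infiltration, compare a named later dam-session reading between arms. Adjust for the first reading only if it precedes the anaesthetic; otherwise the adjustment could remove part of the effect.
6. Label the separate Friedman and within-group Wilcoxon tests as descriptive and draw no comparison from them.
7. State that the change contrast removes only a visit shift constant across readings, so the fixed cotton-roll-first order remains a limitation.

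The cost is SAP wording and one model per measure, with no new data. A plain change score can be noisier than a raw reading when the correlation between readings within a session is below 0.5, which is a reason to prefer the mixed model, or first-reading adjustment where step 5 allows it.
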